8.2 Exclusion Criteria

- 1. Any significant medical co-morbidities which may potentially interfere with participation in or achieving the objectives of the study
- 2. Presence or history of severe mental illness that means the participant is unable to use Salurate independently
- 3. Any significant learning disability that means the participant is unable to use Salurate independently
- 4. Educational status or language barrier that influences capacity to use the App or understand the IFUs
- 5. Women who are physically incapacitated such as to make manipulation of the sampling system uncomfortable or impractical, as judged by the recruiter
- 6. Women who do not have access to a smartphone and/or internet data at home
- 7. Women who have been diagnosed with severe gingivitis or periodontal disease
- 8. Women who have been diagnosed with oral cancer

8.3 Contraindications

- 1. The potential participant suffers from severe nausea and vomiting in pregnancy.
- 2. The potential participant has infected, inflamed, cut/scraped or painful areas in their mouth.

9 INFORMED CONSENT

It is the responsibility of the research team to obtain informed consent for each trial participant.

Informed consent will be obtained during the early scan appointment. The recruiting clinician will allow the potential recruit sufficient time to read consent form *HR-P-51*, *Consent Form* and will have an opportunity to ask questions. If they decide to proceed and join the study, they will be asked to sign the Consent Form. This form will be scanned and stored with the participants' documentation on the EDGE database. Copies of the consent form will be given to the participant and stored in the participant's medical record. Reford of consent will also be entered onto the CRF (Doc: HR-P-55).

¹ Risk assessment based on: maternal factors, Mean Arterial Pressure, Uterine Artery Pulsatility Index, maternal serum pregnancy-associated plasma protein – A and placental growth factors

10 SCHEDULE OF EVENTS

10.1 Preparation

MIAT and its subcontractors will secure components, materials, and will assemble approximately 5000 Salurate test kits, each containing sufficient components to submit 30 samples. Each kit will be issued with a unique Kit ID number, which in turn will be linked to a batch number for traceability purposes.

These kits will be dispatched to recruiting locations in pre-agreed quantities, and will be refrigerated upon arrival².

10.2 Screening

Prior to the 10-14 week dating scan, the clinical team will have assessed the pregnant woman with regards to her risk of developing HDP. This risk category (Low/Medium/High) will be recorded on her clinical notes and will be used by the recruiting clinician to determine study inclusion.

10.3 Enrolment; 10-14 Week dating scan

Subject to eligibility criteria detailed in section 7, and following consent, the clinician will retrieve a Salurate sampling kit from storage and guide the participant through the process of taking a sample.

The clinician will login to the Salurate Portal and 'register' the kit with the Salurate Secure Server by entering the unique KIT ID. The clinician will enter this same ID onto the CRF and participants' clinical notes – thereby creating the pseudo anonymous link between results and participant.

10.4 Data collection; 10-14 Week dating scan

The following will be recorded on the CRF as part of the Dating Scan:

- Study ID
- Maternal age (at booking)
- Ethnicity
- Height (at booking)
- Weight (at booking)
- Smoking
- Obstetric history (parity, FGR, stillbirth, PE, PTB)
- Medical history (CHT, cardiac, renal or autoimmune disease)
- Blood pressure (MAP and date taken)
- PAPP-A (MoM and date taken)
- CRL (mm and date taken)
- Estimated due date (by scan)
- Uterine Artery PI (left and date taken)
- Uterine Artery PI (right and date taken)
- ASPRE risk for PE <37 weeks

10.5 Data collection; Salurate Testing, Week 12 – Conclusion of pregnancy

Each participant submits weekly samples from enrolment \leq 16 weeks of gestation until conclusion of pregnancy.

Should a test kit be destroyed or otherwise misplaced during the study, replacement kits will be issued and Kit ID information updated accordingly.

² Subject to resources available at each facility, MIAT may supply refrigeration equipment to ensure preservation of product

10.6 End Points (Primary Outcomes); Conclusion of Pregnancy

Clinical diagnoses of the following outcomes will be collected and recorded on the participant's CRF for a period of **6** weeks following the conclusion of pregnancy. Definitions 10.6.1 to 10.6.3.2 based on NICE Clinical Knowledge Summaries. The Salurate study's primary outcome is to predict HDP, the primary conditions of which are defined below.

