5.3 Secondary Objectives

- a) To assess whether Salurate could detect occurrence of other important placentally-mediated outcomes such as fetal growth restriction (FGR) spontaneous preterm birth (sPTB), stillbirth and GDM.
- b) To assess the cost effectiveness of Salurate testing compared to current care methods.
- c) To assess the degree of compliance of pregnant women to a self-sampling weekly Salurate test regimen.
- d) To assess the algorithm efficacy in a demographically diverse population.

Note: the current care methods to diagnose HDP involve assessing blood pressure, proteinuria (diagnosed via urinalysis/24 hour collection), blood test results and/ or PIGF levels.

6 Salurate System

Salurate is a non-invasive, home-use self-sampling system.

A weekly saliva sample is taken in the morning before eating, drinking, or brushing teeth. This sample is applied to a colorimetric test paper (test cartridge). An enzymatic reaction occurs, which producing a purple colour of varying intensities. The intensity of colour change is directly proportional to SUA concentration.

Figure 1. Uric acid linearity and colour intensity

A custom developed smartphone app, used in conjunction with a cloud server, receives the image from the smartphone app and extracts the relevant data. This data is combined with previous weeks' data and presented to the prediction algorithm.

The prediction algorithm is designed to detect patterns in the data that identify whether a hypertensive event is likely to occur in the pregnancy.

Figure 2. Salurate System Overview

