10.6.1 Gestational hypertension

New hypertension presenting after 20 weeks, without significant proteinuria

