- At registration of a participant the linkage of participant Identifiable Information to Participant Study ID will be known only to the recruiter, and will be stored securely by the Investigator, either in a hard-copy register under lock-and-key or electronically under password protection. On completion of the Trial the register of linkage of participant Identifiable Information to Participant Study ID will be destroyed.
- As set out above, the participant will be well informed prior to her consent of the intention to extract certain clinical information from the records of every participant, and record them in a CRF on conclusion of the pregnancy. It will be emphasised that the data extraction will be done by a medical professional, and that the participant whose data goes in the CRF will be identified only by Participant Study ID.
- The information to be included in the CRF will be the presence or absence of any of the targeted end-points related to HDP, as defined in this Protocol. These will simply be characterised to the subject as "information relating to the progress and outcome of her pregnancy", but the detailed end-points can be made known on request.
- The completed CRF, identified only by Participant Study ID, will be generated electronically by clinical staff directly into the Sponsor-held data-base, and matched by Participant Study ID with the test-results already on file for the subject holding that Participant Study ID.

At no point will persons other than the participants' clinicians be aware of the subject's ID, or of any clinical information other than that specified in the CRF. The CRF information for a participant pseudonymised by Study ID would be meaningless to an unauthorised observer.

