23 POST-STUDY CARE

The Salurate Study is non-interventional and will cease with the end of pregnancy. Throughout the study and after, participants will receive standard medical care.

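### Section 10.6 collects HDP diagnoses to 6 weeks after pregnancy, but Sections 12 and 23 let the outcome CRF close when pregnancy ends, so HDP diagnosed in between may be recorded as absent

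*Protocol*

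**What the plan says.** Three places in the protocol bear on when the primary outcome is closed.

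- Section 10.6, the end-point section: "Clinical diagnoses of the following outcomes will be collected and recorded on the participant's CRF for a period of" 6 weeks after the pregnancy ends. Its own title is "10.6 End Points (Primary Outcomes); Conclusion of Pregnancy".
- Section 12, under clinical data: information is extracted from each participant's records in order to "record them in a CRF on conclusion of the pregnancy". The next item says that this CRF holds whether or not each HDP end point occurred.
- Section 23: "The Salurate Study is non-interventional and will cease with the end of pregnancy".

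On the test side, Section 10.5 has weekly samples submitted "until conclusion of pregnancy", and Section 6 describes an algorithm meant to "identify whether a hypertensive event is likely to occur in the pregnancy".

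The outcome definitions set a lower limit of 20 weeks and no upper limit. Gestational hypertension, for example, is "New hypertension presenting after 20 weeks, without significant proteinuria". The protocol does not say how HDP first diagnosed after delivery is to be classified.

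Section 15 reports sensitivity, specificity, PPV and NPV of the algorithm against the primary outcome.

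**The concern.** A woman whose HDP is first diagnosed two weeks after delivery is a case under Section 10.6. If her CRF is completed when the pregnancy ends, as Section 12 describes, she is recorded as a non-case. All four accuracy measures depend on which of these happens.

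If she had not been flagged, closing the CRF early turns a false negative into a true negative, which favours the device. If she had been flagged, it turns a true positive into a false positive, which counts against the device.

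A late repair may not be possible. Section 12 describes a record of presence or absence and mentions no date of onset. It also has the register linking identity to Study ID destroyed when the trial is complete. Section 14 ends the study at 4000 complete datasets without saying whether a dataset is complete when pregnancy ends or 6 weeks later.

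**Working it through.** **The plan's own figures.** Section 15 gives N = 4000, 11.5% with any event (PE/PIH/IUGR) and 2.5% with IUGR.

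- 4000 × 0.115 = 460 events; 4000 × 0.025 = 100 IUGR cases. Both match.
- Half-width = 1.96 × √[p(1−p)/n]. For n = 460: 4.6 points at p = 50% and 2.7 at 90%. For n = 100: 9.8 and 5.9. These round to the stated 5, 3, 10 and 6.

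The sample-size text is sound and does not depend on the outcome window.

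**Inputs for the effect of the window.**

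- HDP cases: 460 − 100 = 360, assuming that IUGR and HDP do not overlap. Non-cases: 4000 − 360 = 3640.
- Antenatal sensitivity s = 90% (a value that Section 15 uses) and specificity 90% (assumed).
- f, the share of HDP first diagnosed after delivery: not in the protocol; 5% and 10% assumed, that is 18 and 36 women.
- g, the share of those women flagged before delivery: not in the protocol. Range shown: 10% (the false-positive rate, so no antenatal signal) to 90% (flagged as often as antenatal cases).

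**Sensitivity with the 6-week outcome** = s(1−f) + g·f, against 90% if only antenatal cases count.

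- f = 5%, g = 10%: 0.855 + 0.005 = 86.0%, a drop of 4 points.
- f = 10%, g = 10%: 0.81 + 0.01 = 82.0%, a drop of 8 points.
- g = 90%: 90.0% at either share, no drop.
- Limiting case, f = 10% and none flagged: 81.0%, a drop of 9 points.

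At g = 10% the drop is 0.8f. It passes the stated ±3 points when f exceeds 0.03/0.8 = 3.75%, about 14 of 360 women.

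**NPV, f = 10%, g = 10%.**

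- Antenatal cases 324, missed 32.4. Postpartum cases 36, not flagged 32.4. True negatives 0.90 × 3640 = 3276.
- All test-negatives: 32.4 + 32.4 + 3276 = 3340.8.
- 6-week outcome: 1-NPV = 64.8/3340.8 = 1.9%.
- CRF closed when pregnancy ends: 1-NPV = 32.4/3340.8 = 1.0%.

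At f = 5% and g = 10% the same steps give (34.2 + 16.2)/3326.4 = 1.5% against 34.2/3326.4 = 1.0%. At f = 10% and g = 90% they give 36/3312 = 1.1% against 32.4/3312 = 1.0%.

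**Specificity with the CRF closed when pregnancy ends, f = 10%.**

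- g = 10%: (3276 + 32.4)/(3640 + 36) = 90.0%, unchanged.
- g = 90%: (3276 + 3.6)/3676 = 89.2%.

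**PPV, f = 10%** (antenatal true positives 291.6, false positives 364).

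- g = 10%: 295.2/659.2 = 44.8% with the 6-week outcome, 291.6/659.2 = 44.2% with early closure.
- g = 90%: 324/688 = 47.1% against 291.6/688 = 42.4%.

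So when postpartum cases are rarely flagged, early closure flatters NPV. When they are flagged as often as antenatal cases, NPV hardly changes and the loss falls on PPV.

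**The case against.** The strongest reply is that there is only one end-point rule. Section 10.6 is the specific provision and it is explicit. Its title uses the conclusion of pregnancy as a stage label that covers the 6-week collection, so the same phrase in Section 12 may mean no more than that. The Section 12 wording sits in a data-protection passage about what participants are told, and it refers back to the end points as defined in the protocol. Section 23 concerns post-study care, and Section 11.1.2 keeps contact open for weeks after participation ends, so Section 23 cannot mean that all data collection stops.

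Much of this stands. Section 10.6 should govern, and the conflict may be loose drafting. But Section 12 is where the protocol describes when the outcome CRF is filled in, so its wording can affect practice. The CRF itself is listed in Appendix 1 but not reproduced, so it cannot settle the matter here. Nor can divergence between sites be shown; it is a risk that the wording leaves open.

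A reader might also infer from Section 6 that only HDP before delivery is the right target. The documents do not support that. Sections 5.1 and 5.2 speak of the onset and subsequent development of HDP with no delivery limit, the definitions have no upper limit, and following outcomes past the last test is ordinary in a prediction study.

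**Conclusion.** The point holds as a conflict over when the outcome CRF is closed, with a real risk of misclassifying the primary outcome. It does not invalidate the sample size.

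The clearest consequence of early closure is on NPV: 1-NPV of about 1.0% instead of 1.9% under the illustrative inputs (360 HDP cases, 10% postpartum, 90% antenatal sensitivity, 90% specificity, 10% of postpartum cases flagged). Specificity moves by less than 1 point across the range shown. Counting postpartum cases may lower sensitivity by 0 to about 8 points at a postpartum share of up to 10%. The share and the flagging rate are both assumptions.

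A reader might conclude that every postpartum case is either lost or scored as a device failure. That does not follow: under the 6-week window a woman flagged before delivery is a true positive, and if such women are flagged as often as antenatal cases, sensitivity does not change.

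**What to change.** - Keep the 6-week window of Section 10.6. Amend Sections 12 and 23 so that every outcome CRF is completed at 6 weeks after the pregnancy ends.
- Add a CRF field for whether HDP was first diagnosed before or after delivery, unless the form already captures this.
- Report sensitivity, specificity, PPV and NPV for the 6-week outcome and also for HDP diagnosed before delivery. Which of the two is primary is the sponsor's choice; it should be stated before outcome data are analysed.

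The cost is wording in two sections, at most one CRF field and a second set of accuracy estimates. Each CRF is completed about 6 weeks after delivery, which Section 10.6 already implies.

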10.6.1 Gestational hypertension

New hypertension presenting after 20 weeks, without significant proteinuria

10.6.2 Pre-eclampsia

New onset hypertension presenting after 20 weeks, *and* the coexistence of 1 or more of the following new-onset conditions.

New onset of hypertension (over 140 mmHg systolic or over 90 mmHg diastolic) after 20 weeks of pregnancy and the coexistence of 1 or more of the following new-onset conditions:

- Proteinuria
- Other maternal organ dysfunction:
 - $\circ~$ Renal insufficiency (creatinine 90 micromol/litre or more, 1.02 mg/100 ml or more).
 - Liver involvement (elevated transaminases [alanine aminotransferase or aspartate aminotransferase over 40 IU/litre] with or without right upper quadrant or epigastric abdominal pain).
 - Neurological complications such as eclampsia, altered mental status, blindness, stroke, clonus, severe headaches or persistent visual scotomata.
 - Haematological complications such as thrombocytopenia (platelet count below 150,000/microlitre), disseminated intravascular coagulation or haemolysis
 - Uteroplacental dysfunction such as fetal growth restriction, abnormal umbilical artery doppler waveform analysis, or stillbirth.

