10.7.4 Definition of HDP

Blood Pressure

- Systolic blood pressure ≥130 mm Hg on 1 or more occasions
- Diastolic blood pressure ≥80 mm Hg on 1 or more occasions

Urine

- Urine protein dipstick test 1+ or more
- Urinary protein/creatinine ratio ≥0.30 mg/mg
- Urinary protein ≥300 mg per day in timed collection

Bloods

- New-onset low platelet count ≤100,000 x 109/L
- New onset elevated serum creatinine ≥1.0 mg/dL
- New-onset transaminase elevation above limits of normal for local laboratory

Symptoms

- New-onset headache unresponsive to medication and not accounted for by alternative diagnoses
- New-onset visual symptoms

Fetus

- Fetal growth restriction with AC/estimated fetal weight ≤10th percentile

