15 STATISTICAL CONSIDERATIONS

A cohort of 4,000 participant mothers would experience an estimated 460 events overall (PE/PIH/ IUGR) assuming a prevalence of 11.5%, and 100 cases of IUGR (the least prevalent of the conditions being studied), assuming a prevalence of 2.5%, based on observations from the Denmark study. This sized cohort would allow sensitivity of the Salurate algorithm to identify IUGR to be estimated with a 2-sided 95% confidence interval (CI) to within plus or minus 10% of the point estimate (if sensitivity was actually 50%, i.e. 95% CI 40% - 60%) and this would improve to a more precise confidence interval to within plus or minus 6% of the point estimate if the sensitivity proved to be around 90% (i.e. 95% CI 84% - 96%).

Additionally, a cohort of N=4,000 would allow sensitivity of the Salurate algorithm to identify any of the events of interest (prevalence 11.5%) to be estimated with greater precision, with a 2-sided 95% confidence interval to within plus or minus 5% of the point estimate (if sensitivity was actually 50%, i.e. 95% CI 45% - 55%) and this would improve to a more precise confidence interval to within plus or minus 3% of the point estimate if the sensitivity proved to be around 90% (i.e. 95% CI 87% - 93%). Specificity will be estimated to a much higher degree of precision because the majority of participants/babies in the cohort will not encounter adverse outcomes, and so they will comprise the much larger sample.

All analysis will be conducted by the study statistician Professor [name], using StataSE v16.1 statistical analysis software.

The Salurate study is quantitative research (numerical outcome). The quantitative data for this study will be analysed and reported according to the relevant reporting guidelines (STARD, BMJ. 2015;351:h5527. PMID: 26511519 and TRIPOD BMJ 2015; 350:g7594. PMID: 25569120).

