All clinical primary and secondary outcomes (maternal and neonatal) will be presented across the whole cohort as percentages with 95% confidence intervals, missing outcomes data will be presented. Women's characteristics at enrolment into the study will also be presented with percentages or summary statistics as appropriate. Salivary uric acid concentration (Salurate) observations will be presented graphically over time from the initial 10-14 week pregnancy record through to the end of study participation i) for the whole cohort, ii) by primary outcome (HDP present or absent), iii) for each secondary outcome, including adverse maternal or perinatal outcomes.

Numbers and percentages of missing Salurate reports will be presented by week of pregnancy with the number of women participating in the study as the denominator (which may vary in the last weeks of the study depending on when they give birth). This will be used to assess the degree of compliance of women to the testing regime. No multiple imputation or other forms of missing data replacement will be used to estimate missing values of Salurate. No missing data replacement will be employed for clinical outcomes or participant's characteristics at enrolment, and every effort will be made to record these data. We anticipate that rates of data missingness will be low.

Multilevel Logistic/Linear regression models, as appropriate, will be used to determine the relationship between Salurate results and the primary and secondary outcomes in this cohort. The Salurate algorithm will be employed and its sensitivity, specificity, positive predictive value (PPV) and negative predictive value (NPV) to identify the primary outcome will be presented with 95% confidence intervals. We will also determine how soon the primary outcome would be indicated using Salurate results and compare this with traditional prediction methods using standard NHS monitoring data.Subgroup analyses will explore whether the Salurate algorithm has greater diagnostic value in particular women according to baseline characteristics, although these analyses may not have enough statistical power to be definitive. Adverse Event and Serious Adverse Events details will be listed.

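### Section 15 does not separate FGR and stillbirth by HDP status, so a test that tracks only HDP could appear to detect these other outcomes

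*Protocol*

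**What the plan says.** Four parts of the protocol bear on this.

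- **Objective.** Section 5.3(a) asks about "other important placentally-mediated outcomes such as fetal growth restriction (FGR) spontaneous preterm birth (sPTB), stillbirth and GDM". The contrast is with HDP, the primary outcome.
- **Definition of pre-eclampsia.** Section 10.6.2 requires new hypertension after 20 weeks together with at least one further new condition. One of these is "Uteroplacental dysfunction such as fetal growth restriction, abnormal umbilical artery doppler waveform analysis, or stillbirth". Section 10.6.1 already counts as gestational hypertension, and so as HDP: "New hypertension presenting after 20 weeks, without significant proteinuria".
- **A second definition.** Section 10.7.4, headed as a definition of HDP, lists "Fetal growth restriction with AC/estimated fetal weight ≤10th percentile" without saying whether hypertension must also be present.
- **Analysis.** Section 15 expects 460 events of any kind (PE, PIH or IUGR) and 100 of IUGR among 4,000 women, and says: "This sized cohort would allow sensitivity of the Salurate algorithm to identify IUGR to be estimated". Regression models are to "determine the relationship between Salurate results and the primary and secondary outcomes in this cohort". The only subgroups named are by baseline characteristics. HDP status does not appear as a stratum, restriction or covariate.

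**The concern.** If some women with FGR or stillbirth also have HDP, a test that alarms for HDP will alarm in those women. Their alarms then count towards sensitivity for FGR, and the regression shows an association with FGR, even if the test carries no information about fetal growth. Read on its own, the pooled result cannot separate detection of FGR from detection of the HDP that accompanies it.

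At stake is the interpretation of secondary objective (a). The accuracy figures for the primary outcome are not affected.

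**Working it through.** **1. The plan's own figures.** From Section 15: 4,000 × 11.5% = 460 events and 4,000 × 2.5% = 100 IUGR cases. The Wald half-width is 1.96 × √(p(1−p)/n).

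- n = 100: 9.8 points at p = 50% and 5.9 at p = 90% (stated ±10 and ±6).
- n = 460: 4.6 and 2.7 points (stated ±5 and ±3).

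The stated figures reproduce. The ±10 for IUGR uses all 100 cases, with or without HDP.

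**2. What the plan implies about overlap.** Let f be the share of IUGR cases that also have HDP. Taking the 460 events as distinct women (an assumption), any event = HDP + IUGR − both. So f = (HDP prevalence − 9.0%)/2.5%.

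- HDP 9.0% gives f = 0.
- HDP 10% gives f = 40%.
- HDP 11.5% gives f = 100%.

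Section 15 gives no separate HDP prevalence. The 10% is the worldwide figure in Section 4.1, which includes chronic hypertension, so it only illustrates how wide the range is.

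**3. A test that knows only HDP.** Assume alarms in 80% of women with HDP and 10% of all others, whatever the fetal growth.

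- Women without IUGR: 4,000 − 100 = 3,900, of whom 460 − 100 = 360 have HDP (9.2%). Alarm rate = (360/3,900) × 0.8 + (3,540/3,900) × 0.1 = 16.5%.
- Women with IUGR: alarm rate = f × 0.8 + (1 − f) × 0.1.
- Odds ratio = [p/(1−p)] / [0.165/0.835], with p the rate in women with IUGR.

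| f (assumed) | Alarm rate in IUGR | Alarm rate without IUGR | Odds ratio |
|---|---|---|---|
| 9% | 16% | 16.5% | about 1.0 |
| 20% | 24% | 16.5% | 1.6 |
| 30% | 31% | 16.5% | 2.3 |
| 50% | 45% | 16.5% | 4.2 |

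Within women with HDP, and within women without it, the odds ratio is 1.0 by construction. A split by HDP status therefore removes the artefact. Below about 9% overlap the artefact runs the other way, with odds ratios under 1.

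**4. Other assumed accuracies**, keeping 10% alarms in women without HDP. The last column is the chance of a significant difference (two-sided 5%, 100 against 3,900 women).

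| Alarms in HDP | f | Odds ratio | Chance of significance |
|---|---|---|---|
| 90% | 20% | 1.7 | 59% |
| 90% | 30% | 2.5 | 97% |
| 50% | 20% | 1.4 | 26% |
| 50% | 30% | 1.8 | 64% |

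**5. Precision in HDP-free cases**, at 50% sensitivity.

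- 80 cases left (f = 20%): 1.96 × √(0.25/80) = 11.0 points.
- 50 cases left (f = 50%): 1.96 × √(0.25/50) = 13.9 points.

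**The case against.** The strongest counter-arguments, and what stands of each:

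- **The criterion in 10.6.2 does not create the overlap.** A reader might infer that listing FGR and stillbirth there builds secondary outcomes into the primary one. The text does not support that. New hypertension is required as well, and without proteinuria it is already HDP under 10.6.1. The criterion mainly moves a woman from one HDP subtype to another. This stands: the problem is co-occurrence.
- **Detecting FGR in a woman with HDP is still detecting FGR.** Whole-cohort sensitivity is a valid description and should be kept. It does not show detection beyond HDP, which is what the contrast in 5.3(a) invites readers to conclude.
- **The split could be in the SAP.** The models list no covariates, and sensitivity, specificity, PPV and NPV are promised explicitly only for the primary outcome. An unseen SAP could add the split. The protocol's IUGR precision would still rest on all 100 cases.
- **No success rule exists for 5.3(a).** This stands. The text does not support saying that the objective would be declared met, only that a pooled association could be read that way.
- **The HDP-free subset selects on a later outcome.** This also stands. HDP status is unknown when the test is used, so that subset cannot be the only answer.
- **The endpoints are not identical.** Section 10.7.1 defines SGA by birth weight, not FGR. Stillbirth is not listed in 10.7 and would fall under adverse perinatal outcomes in 10.6.4. The overlap question is the same for each.

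**Conclusion.** The point holds as a matter of interpretation for a secondary objective. As written, Section 15 cannot tell a test that detects FGR or stillbirth from one that detects only the accompanying HDP.

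The size is conditional. The overlap and the alarm rates are assumptions, and the 460 events are taken as distinct women. On the 80% and 10% alarm rates, the spurious odds ratio is negligible at about 9% overlap and runs from 1.6 to 4.2 between 20% and 50%.

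A reader might also infer from 10.7.4 that FGR alone makes a woman an HDP case, which would leave no FGR outside HDP. The section does not say whether its items are alternatives or must be combined with hypertension. It therefore supports only the need to reconcile it with 10.6.

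**What to change.** 1. Reconcile Section 10.7.4 with Section 10.6, so that it is clear which women count as being without HDP and whether FGR in the absence of hypertension is among the HDP criteria.
2. In Section 15, report sensitivity, specificity and the regression result for FGR/SGA and for stillbirth separately in women with and without HDP, beside the whole-cohort figure. Rest any claim of detection beyond HDP on the HDP-free result.
3. State the expected IUGR precision for HDP-free cases next to the ±10 for all 100, with the assumed number of cases: about ±11 points for 80 and ±14 for 50, at 50% sensitivity.

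No new data are needed, since HDP diagnoses and pregnancy outcomes are already to be collected. The cost is a wider interval in the HDP-free group. The whole-cohort figure should stay, because HDP status is known only later in pregnancy.
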